10.3.3.1.6 Twelve-lead Electrocardiogram

All subjects will undergo ECGs as indicated in the schedule of assessments. Where applicable, digital ECGs will be collected using the ECG equipment delivered by the central ECG laboratory (ECG lab) and will be transferred to and analysed by the ECG lab according to the lab's standard operating procedures. Further details are provided in the ECG Manual.

Paper printouts of the 12-lead ECGs will be reviewed in real time by the principal investigator, or delegate, for safety monitoring. The results of the evaluation will be reported in the eCRF as *normal* or *abnormal* (if abnormal, the ECG is also to be reported as not clinically significant or clinically significant). The details of any ECG abnormalities should be described and captured in the eCRF (irrespective of whether they are considered not clinically significant or clinically significant).

10.3.3.1.7 Physical and Neurological Examination

A complete physical and neurological examination (excluding the genitourinary examination, unless warranted) will be performed at Screening, Week 12, and Week 18/Early Termination, as indicated in the schedule of assessments.

A targeted physical and neurological examination based on symptoms and previous findings will be performed at all other visits.

Height and weight will be measured at Screening.

10.3.3.1.8 Total Neuropathy Scores--Nurse

The TNSn, a semi-quantitative clinical assessment of peripheral nervous system function, will be administered at Screening, Day 1, Week 2, Week 4, Week 6, Week 8, Week 10, Week 12 and Week 18/Early Termination. The TNSn provides for an assessment of motor symptoms, autonomic symptoms, pin sensibility, vibration sensibility, and deep tendon reflexes. Strength (dorsiflexion) and deep tendon reflexes (knee and ankle) are to be scored at every visit alongside the TNSn assessments.

10.3.3.1.9 Motor and Sensory Nerve Conduction Studies

Motor and sensory NCS will be undertaken in relevant lower and upper limb nerves (sural, peroneal, and median/ulnar nerves). Relevant endpoints including peak latency, amplitude, conduction velocity and duration of nerve action potentials will be captured using standard antidromic or orthodromic determination according to protocol and will be recorded at baseline and at the follow-up visit.

10.3.3.1.10 Injection Site or Infusion Reactions

Investigators should evaluate infusion reactions that occur during or immediately following infusion per the FDA Guidance for Industry, Immunogenicity Assessment for Therapeutic Protein Products (2014) and FDA Guidance for Industry, Toxicity Grading Scale for Healthy Adult and Adolescent Volunteers Enrolled in Preventive Vaccine Clinical Trials (2007). 42,43 See Section 5.3 for discussion of potential infusion reactions.

Investigators should evaluate injection site reactions using the toxicity grading scale summarized in Table 10-1.

Table 10-1: Local Reactions to Injectable Product

Local Reaction	Mild	Moderate	Severe
Pain	Does not interfere	Repeated use of non-narcotic	Any use of narcotic pain
	with activity	pain reliever >24 hours or	reliever or prevents daily
		interferes with activity	activity
Tenderness	Mild discomfort to touch	Discomfort with movement	Significant
			discomfort at rest
Erythema/redness ^a	2.5 to 5 cm	5.1 to 10 cm	>10 cm
Induration/swelling ^b	2.5 to 5 cm and does not	5.1 to 10 cm or interferes	>10 cm or prevents daily
	interfere with activity	with activity	activity

Source: FDA 2007⁴³

10.3.3.2 Adverse Events

The definitions and management of AEs, and any special considerations for AEs, are provided in Section 11.

a In addition to grading the measured local reaction at the greatest single diameter, the measurement should be recorded as a continuous variable.

b Induration/swelling should be evaluated and graded using the functional scale as well as the actual measurement.

11 ADVERSE EVENTS

11.1 Definitions

11.1.1 Adverse Events

An AE is defined as any untoward medical occurrence in a patient or clinical investigation subject administered a pharmaceutical product that does not necessarily have a causal relationship with this treatment. An AE can therefore be any unfavourable and unintended sign (including an abnormal laboratory finding, for example), symptom, or disease temporally associated with the use of a medicinal product, whether or not related to the medicinal product.

Pre-existing diseases or conditions will not be considered AEs unless there is an increase in the frequency or severity, or a change in the quality, of the disease or condition. (Worsening of a pre-existing condition is considered an AE.)

Events that occur in subjects treated with placebo, or during treatment-free periods of the study, are also considered AEs.

11.1.2 Adverse Drug Reaction

All noxious and unintended responses to an IP related to any dose should be considered adverse drug reactions (ADRs).

The phrase "responses to an investigational product" means that a causal relationship between an IP and an AE is at least a reasonable possibility, ie, the relationship cannot be ruled out. All AEs judged by either the reporting investigator or the sponsor as having a reasonable causal relationship to an IP qualify as ADRs.

All AEs for which the judgment of relationship to IP is "possible" or higher will be considered ADRs. If a relationship to IP is not provided, then the AE must be treated as if it were "possible".

11.1.3 Unexpected Adverse Event/Adverse Drug Reaction

An expected AE or ADR is one for which the nature or severity is consistent with the known AE profile of the product. For a pre-approval test product, the known information is contained in the IB. For a marketed product, the known information is contained in the current package insert for the product.

An unexpected AE or unexpected adverse drug reaction (UADR) is one for which the nature or severity of which is not consistent with the applicable product information (eg, Investigator's Brochure for an unapproved IP or package insert/summary of product characteristics for an approved product). For example, hepatic necrosis would be unexpected (greater severity) if the IB only listed elevated hepatic enzymes or hepatitis. Likewise, cerebral thromboembolism and cerebral vasculitis would be unexpected (greater specificity) if the IB only listed cerebral vascular accidents.

Furthermore, reports that add significant information on specificity or severity of a known, already documented adverse reaction constitute unexpected events. Examples would be (a) acute renal failure as an expected adverse reaction with a subsequent new occurrence of interstitial nephritis (interstitial nephritis would be unexpected) and (b) hepatitis with a first occurrence of fulminant hepatitis (fulminant hepatitis would be unexpected.)

11.1.4 Serious Adverse Events

An SAE is any untoward medical occurrence that at any dose:

- results in death
- is life-threatening

NOTE: The term "life-threatening" in the definition of "serious" refers to an event in which the patient was at risk of death at the time of the event; it does not refer to an event that hypothetically might have caused death if it were more severe.

• requires inpatient hospitalization or prolongation of existing hospitalization

NOTE: Outpatient treatment in an emergency room is not in itself a serious AE, although the reasons for it may be (eg, bronchospasm, laryngeal oedema). Hospital admissions and/or surgical operations planned before or during a study are not considered AEs if the illness or disease existed before the subject was enrolled in the study, provided that it did not deteriorate in an unexpected way during the study.

- results in persistent or significant disability/incapacity
- is a congenital anomaly

NOTE: A congenital anomaly in an infant born to a mother who was exposed to the IP during pregnancy is an SAE. However, a newly diagnosed pregnancy in a subject that has received an IP is not considered an SAE unless it is suspected that the IP(s) interacted with a contraceptive method and led to the pregnancy.

• is an important medical event

NOTE: Medical and scientific judgment should be exercised in deciding whether it is appropriate to consider other situations serious, such as important medical events that may not be immediately life-threatening or result in death or hospitalization but may jeopardize the patient or may require intervention to prevent one of the other outcomes listed in the definition above. Examples of such events are intensive treatment in an emergency room or at home for allergic bronchospasm, blood dyscrasias, or convulsions that do not result in hospitalization, development of drug dependency, or drug abuse. The occurrence of malignant tumors is also to be considered serious.

11.1.5 Significant Adverse Events

13-Apr-2022

Other significant AEs are defined as marked haematological and other laboratory abnormalities (other than those meeting the definition of serious) and any events that led to an intervention, including withdrawal of test drug, dose reduction, or significant additional concomitant therapy.

11.1.6 Treatment-Emergent Adverse Events

An AE is defined as treatment-emergent if the first onset or worsening is after the first administration of IP and not more than 30 days after the last administration of IP.

11.2 Event Assessment and Follow-up of Adverse Events

The occurrence of an AE or SAE may come to the attention of study personnel during study visits and interviews of a study participant presenting for medical care, or upon review by a study monitor.

All AEs including local and systemic reactions not meeting the criteria for SAEs will be captured on the appropriate eCRF. Information to be collected includes event description, time of onset, clinician's assessment of severity, relationship to study product (assessed only by those with the training and authority to make a diagnosis), and time of resolution/stabilization of the event. All AEs occurring while on study must be documented appropriately regardless of relationship. All AEs will be followed to adequate resolution.

Any medical condition that is present at the time that the participant is screened will be considered as baseline and not reported as an AE. However, if the study participant's condition deteriorates at any time during the study, it will be recorded as an AE.

Changes in the severity of an AE will be documented to allow an assessment of the duration of the event at each level of severity to be performed. AEs characterized as intermittent require documentation of onset and duration of each episode.

The site staff will record all reportable events with start dates occurring any time after informed consent is obtained until 7 (for nonserious AEs) or 30 days (for SAEs) after the last day of study participation. At each study visit, the investigator will inquire about the occurrence of AE/SAEs since the last visit. Events will be followed for outcome information until resolution or stabilization.

11.2.1 Assessment

The investigator is responsible for the detection and documentation of events meeting the criteria and definition of an AE or SAE described previously. At each visit, the subject will be allowed time to spontaneously report any issues since the last visit or evaluation. The investigator will then monitor and/or ask about or evaluate AEs using nonleading questions, such as

- "How are you feeling?"
- "Have you experienced any issues since your last visit?"
- "Have you taken any new medications since your last visit?"

Any clinically relevant observations made during the visit will also be considered AEs.

743 of 938 Page 70 of 114

11.2.2 Evaluation

11.2.2.1 Severity of Adverse Events

The clinical severity of an AE will be classified as:

Mild Usually transient and may require only minimal treatment or therapeutic

intervention. The event does not generally interfere with usual activities of

daily living.

Moderate Usually alleviated with additional specific therapeutic intervention. The event

interferes with usual activities of daily living, causing discomfort but poses no

significant or permanent risk of harm to the subject.

Severe Interrupts usual activities of daily living, or significantly affects clinical status,

or may require intensive therapeutic intervention.

It is important to distinguish between severe AEs and SAEs. Severity is a classification of intensity whereas an SAE is an AE that meets serious criteria, as described in Section 11.1.4.

11.2.2.2 Seriousness

The investigator is to evaluate whether the AE meets serious criteria, as described in Section 11.1.4.

11.2.2.3 Action(s) Taken

Action(s) taken may consist of:

Dose increased An indication that a medication schedule was modified by addition; either

by changing the frequency, strength, or amount.

Dose not changed An indication that a medication schedule was maintained.

Dose reduced An indication that a medication schedule was modified by subtraction,

either by changing the frequency, strength, or amount.

Drug interrupted An indication that a medication schedule was modified by temporarily

terminating a prescribed regimen of medication.

Drug withdrawn An indication that a medication schedule was modified through

termination of a prescribed regimen of medication.

Not applicable Determination of a value is not relevant in the current context.

Unknown Not known, not observed, not recorded, or refused.

11.2.2.4 Outcome at the Time of Last Observation

The outcome at the time of last observation will be classified as:

- Recovered/resolved
- Recovered/resolved with sequelae
- Recovering/resolving
- Not recovered/not resolved

- Fatal*
- Unknown

*Only select fatal as an outcome when the AE results in death. If more than one AE is judged to be possibly related to the subject's death, the outcome of death should be indicated for each such AE. [Although "fatal" is usually an event outcome, events such as sudden death or unexplained death should be reported as SAEs.]

11.2.2.5 Adverse Event Relationship to Investigational Product

The investigator must make an assessment of each AE's relationship to the IP. The categories for classifying the investigator's opinion of the relationship are as follows:

Related A reasonable possibility exists of a relationship between the AE and IP.

Not related No reasonable possibility exists of a relationship between the AE and IP.

11.2.3 Documentation

All AEs that occur within the period of observation for the study must be documented in the CRF with the following information, where appropriate. (The period of observation for the study is described in Section 11.2.)

- AE name or term
- When the AE first occurred (start date and time)
- When the AE stopped (stop date and time or an indication of "ongoing")
- Severity of the AE
- Seriousness (hospitalization, death, etc.)
- Actions taken
- Outcome
- Investigator opinion regarding the AE relationship to the IP(s)

11.2.4 Treatment of Adverse Events

Adverse events that occur during the study will be treated, if necessary, by established standards of care. If such treatment constitutes a deviation from the protocol, the decision about whether the subject may continue in the study will be made by the sponsor after consultation with the investigator and/or medical monitor.

If AEs occur in a subject that are not tolerable, the investigator must decide whether to stop the subject's involvement in the study and/or treat the subject. Special procedures may be recommended for the specific IP, such as the collection of a serum sample for determining blood concentrations of IP, specific tapering procedures, or treatment regimens, as appropriate.

For double-blinded studies, it is not necessary to unblind a subject's treatment assignment in most circumstances, even if an SAE has occurred. If unblinding is necessary, see Section 9.6 for a description of the unblinding procedures.

11.2.5 Follow-up

Any AE will be followed to a satisfactory resolution, until it becomes stable, or until it can be explained by another known cause(s) (ie, concurrent condition or medication) and clinical judgment indicates that further evaluation is not warranted. All findings relevant to the final outcome of an AE must be reported in the subject's medical record and recorded on the eCRF.

11.2.6 Reporting

11.2.6.1 Serious Adverse Events

The investigator or designee must report all SAEs promptly to MMS Holdings Inc. (MMS) within 24 hours of first becoming aware of the event by completing, signing and dating the Serious Adverse Event Report Form, verifying the accuracy of the information recorded in the form with the source documents and eCRF, and sending the SAE form to MMS by one of the following methods:

Email: [contact]

[contact]

This written report should be submitted on the SAE form provided for this purpose. At the time of first notification, the investigator or designee should provide the following information, if available:

- Protocol number
- Reporter (study site and investigator)
- Suspect IP
- Subject's study number
- Subject's year of birth
- Subject's gender
- Date of first dose of IP
- Date of last dose of IP, if applicable
- Adverse event term

13-Apr-2022

- Date of occurrence of the event
- A brief description of the event, outcome to date, and any actions taken
- The seriousness criteria that were met
- Concomitant medication at onset of the event

- Relevant medical history information
- Relevant laboratory test findings
- Investigator's opinion of the relationship to IP ("Is there a reasonable possibility that the IP caused the SAE? Yes or No?")
- Whether and when the investigator was unblinded as to the subject's treatment assignment

Any missing or additional relevant follow-up information concerning the SAE should be sent to the sponsor/sponsor representative via the same contact details above as soon as possible on a follow-up SAE Report Form, together with the following minimal information (initial report, AE, date of occurrence, subject identification (ID), study ID, IP, and site number); this will allow the follow-up information to be linked to the initial SAE report.

Specific information may be requested by the MMS Pharmacovigilance Department using a follow-up request form or via email communication.

The investigator is required to comply with applicable regulations (including local laws and guidances) regarding the notification of his or her health authorities, institutional review board (IRB)/independent ethics committee (IEC), principal and coordinating investigators, study investigators, and institutions. Each investigator is obligated to learn about the reporting requirements for investigators in his/her country.

11.2.6.2 Adverse Drug Reactions

All ADRs should be reported by the investigator in the eCRF.

Suspected serious ADRs must be reported to the sponsor immediately, regardless of the time elapsed since the end of the observation period.

11.2.6.3 Nonserious Adverse Events

Nonserious AEs will be recorded in the eCRF and reported by Premier Research to the sponsor according to the Safety Management Plan.

11.3 Special Considerations

11.3.1 Adverse Events of Special Interest

An AESI is a treatment-emergent AE of scientific and medical interest specific to understanding of the effects of the IP and may require close monitoring and collection of additional information by the investigator. An AESI may be serious or nonserious. The rapid reporting of AESIs allows ongoing surveillance of these events in order to characterise and understand them in association with the use of MEDI7352.

Refer to Section 5.3 for a summary of potential risks and the IB for a detailed discussion of potential risks.

The following AESIs have been identified specifically for this MEDI7352 protocol and are to be reported as described in Section 11.2.6.1.

747 of 938 Page 74 of 114

- Positively-adjudicated possible or probable RPOA, subchondral insufficiency fractures, primary osteonecrosis, or pathological fracture
- Infections that meet SAE or severe AE criteria*
- Anaphylactic reactions or infusion-related reactions that lead to permanent discontinuation of administration of IP

Adverse events of special interest irrespective of their severity and seriousness should be reported immediately using the same procedure as for SAE reporting (Section 11.2.6.1).

*Note: A serious infection is any infection that meets the SAE criteria in Section 11.1.4. Serious infection AEs should be reported as SAEs. A severe infection is any infection that does not meet SAE criteria but is incapacitating, with inability to perform normal activities. Non-serious severe infections are reported as AEs. It is expected that microorganism culture results and all diagnostic or therapeutic procedure results performed on a study participant experiencing a serious or severe infection will be provided as an SAE/AESI update.

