8.2.2 Exclusion Criteria

A subject will be excluded from the study if he or she meets any of the following criteria:

General

- 1. Requires current treatment with another biologic therapeutic agent.
- 2. Previously received any form of anti-NGF or anti-TNF therapy.

- 3. Participation in another clinical study with an IP or device within 60 days or 5 half-lives prior to screening, whichever is longer.
- 4. Plasma donation within 28 days of screening or any blood donation or blood loss >500 mL within 2 months of screening.
- 5. Previous allogeneic bone marrow or stem cell transplant.
- 6. Received non-leukocyte-depleted whole blood transfusion within 120 days of the genetic research sample collection, if participating in the optional genetic research.
- 7. Poor venous access such that IV drug delivery would be difficult.
- 8. Involvement in the planning and/or conduct of the study (applies to both AstraZeneca staff and staff at the study site) and in accordance with local regulations.

Medical history

- 9. Presence of other clinically significant neuropathy (eg, hereditary neuropathy, inflammatory neuropathy) or other clinically significant disorder (eg, nerve compression injury) involving abnormal peripheral sensation, with an aetiology that is considered to be distinct from that of PDN, and that is likely to interfere with assessment of peripheral nerve function, as judged by the investigator.
- 10. History of osteonecrosis, rapidly progressive OA, subchondral insufficiency fractures, neurogenic arthropathy, or analgesia-induced arthropathy.
- 11. Diagnosis of clinically significant OA currently affecting a major joint in the upper extremity (shoulder, elbow, or wrist) or lower extremity (hip, knee, or ankle) or axial spine; or other degenerative disease affecting any joint in subjects for whom, in the opinion of the investigator, there is an identified risk of osteonecrosis, rapidly progressive OA, subchondral insufficiency fractures, neurogenic arthropathy, or analgesia-induced arthropathy.

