 - NOTE: The diagnosis and evaluation of OA should be guided by American College of Rheumatology (ACR)-endorsed criteria, where applicable, and should incorporate radiologic investigation for the assessment of OA severity consistent with the relevant ACR guidance (Altman et al. 1986, Altman et al. 1990, Altman et al. 1991)^{35,36,37} at the discretion of the investigator, or otherwise guided by local rheumatologic, orthopaedic, or radiologic expert advice. Where Kellgren and Lawrence grading is used for the radiographic evaluation of major joint OA, grade ≥2 would be considered exclusionary for trial participation. In subjects for whom there is evidence of clinically significant sensory impairment in the distal lower extremity (based on medical history, clinical examination, TNSn, or evidence of sensory nerve conduction impairment available from NCS), there is an absolute requirement for bilateral feet and ankle radiographs to be undertaken for the evaluation of OA severity to exclude the possibility of neuropathic arthropathy. All radiologic investigations should be reported locally and the reports should be retained in the patient files as source documentation and made available in the event that subsequent adjudication of rheumatologic adverse events is required. Radiologic images should also be retained and made available in the event that subsequent adjudication of rheumatologic adverse events is required.
- 12. Chronic pain condition, other than PDN, that is likely to interfere with the evaluation of the subject's PDN pain, as judged by the investigator.

- 13. Presence of any major psychiatric disorder according to the criteria of the Diagnostic and Statistical Manual of Mental Disorders, 5th Edition, if, in the opinion of the investigator, the psychiatric disorder or symptom is likely to confound interpretation of drug effect, affect pain assessment, or affect the subject's ability to complete the study.
- 14. Significant cardiovascular disease, including Class 3 or Class 4 (The Criteria Committee of the New York Heart Association (NYHA) classification standards 1994)³⁸ congestive heart failure (ejection fraction of <40%) or clinically significant stenosis or occlusion of a carotid or vertebral artery or clinically significant arrhythmias.

NOTE: Validated NYHA classification standards:

- Class 1: cardiac disease but no symptoms and no limitations in ordinary physical activity (no shortness of breath when walking, climbing stairs)

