9.3.1 Safety Stopping Rules

Safety will be monitored by the study-appointed medical monitors from Premier Research and AstraZeneca throughout the study in accordance with the Medical Monitoring Plan. In addition, an Interim Safety Review of blinded aggregate safety data will be undertaken following completion of follow-up visits for approximately every 30 subjects enrolled in the study and no less frequently than every 3 months. The interim review will be performed by AstraZeneca Neuroscience in conjunction with the pharmacovigilance and safety agent, MMS Holdings in accordance with the Safety Management Plan.

Based on the interim safety reviews of aggregate safety data, the study may be stopped if the risks are found to outweigh the potential benefits.

For any individual subject, further administration of IP will be stopped if any of the following scenarios occur with a reasonable possibility of a causal relationship to administration of MEDI7352:

- Reports of drug-related serious AE (SAE[s]) or drug-related severe AE(s) including (but not necessarily limited to):
 - o Infusion reactions and injection site reactions
 - Worsening of existing cutaneous sensory abnormalities or development of new cutaneous sensation AEs (eg, paraesthesia, dysesthesia, burning, pins and needles) that are considered serious or severe and drug-related
 - o Positively adjudicated destructive arthropathy
 - o Serious systemic infection

AD-MW-07.06 08-Dec-2017 722 of 938 Page 49 of 114

- Anaphylactic reaction, defined as an immediately life-threatening allergic reaction with bronchoconstriction, angioedema, and/or hypotension (refer to FDA Guidance for Industry, Immunogenicity assessment for therapeutic protein products, 2014).⁴²
- o Fulfilling Hy's Law, defined as AST or ALT $\ge 3 \times \text{ULN}$ and bilirubin $\ge 2 \times \text{ULN}$, in the absence of a significant increase in alkaline phosphatase (ALP) and in the absence of an alternative diagnosis that could explain the increase in bilirubin
- O Severe autonomic AEs, including but not limited to symptomatic orthostatic hypotension and orthostatic intolerance, that are considered drug-related
- o Renal toxicity, defined as serum creatinine $\geq 1.5 \times \text{ULN}$
- o Haematologic toxicity, defined as one or more of the following:
 - Leukocyte count $< 2.0 \times 10^9/L$
 - Neutrophil count $<1.0 \times 10^9/L$
 - Platelet count $< 75 \times 10^9 / L$

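### The joint-safety AESI is defined by an adjudication result, so a nonserious suspected joint event falls outside the immediate reporting that Section 11.3.1 requires, and its terms do not match the stopping rule in Section 9.3.1

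*Protocol*

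**What the plan says.** Section 11.3.1 gives the purpose of the AESI category: "The rapid reporting of AESIs allows ongoing surveillance of these events". It allows an AESI to be serious or nonserious and then sets the duty: "Adverse events of special interest irrespective of their severity and seriousness should be reported immediately using the same procedure as for SAE reporting". The procedure referred to, in Section 11.2.6.1, runs to 24 hours from first awareness. The joint-safety entry in the AESI list reads "Positively-adjudicated possible or probable RPOA, subchondral insufficiency fractures, primary osteonecrosis, or pathological fracture".

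Section 9.3.1 lists the events that stop further dosing in an individual subject. The parent criterion is a drug-related serious or severe adverse event, "including (but not necessarily limited to") a set of examples. The joint example is "Positively adjudicated destructive arthropathy".

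Section 8.2.2 treats joint disease at entry. Criterion 10 excludes subjects with "History of osteonecrosis, rapidly progressive OA, subchondral insufficiency fractures, neurogenic arthropathy, or analgesia-induced arthropathy". The note to criterion 11 requires foot and ankle radiographs in subjects with clinically significant distal sensory impairment, "to exclude the possibility of neuropathic arthropathy". The reports and images are to be kept and "made available in the event that subsequent adjudication of rheumatologic adverse events is required".

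**The concern.** An AESI category adds something mainly for nonserious events, because serious ones already travel by the expedited route. For joint events the definition undoes that benefit. The investigator must report immediately, but what is to be reported comes into being only after someone else has reviewed the case and found it positive. An investigator who follows the text has no duty of immediate reporting for a nonserious suspected event.

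This concerns a risk that the protocol takes seriously. Section 5.3 names infrequent cases of rapidly progressive osteoarthritis (RPOA) as the most significant adverse effect of anti-NGF antibodies and adds that the joint risk extends beyond osteoarthritic joints. Every subject has diabetic neuropathy, the trial has no data safety monitoring board (Section 12), and no legible row of the schedule in Table 2-1 provides for joint imaging during the study. Detection therefore rests largely on adverse event reports.

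A second problem is that the stopping rule and the AESI list describe joint harm in different words. A site cannot tell from the text which AESI entities would meet the stopping term.

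**Working it through.** No figure in the plan bears on this point, so the check sets the passages side by side.

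**Step 1: order of events.** The reporting clock in Section 11.2.6.1 starts at first awareness. Section 8.2.2 describes adjudication of rheumatologic adverse events as a later, conditional step, so the adverse event exists before adjudication. At the moment the clock starts, no joint event can be positively adjudicated. The other two AESI entries (serious or severe infections; anaphylactic or infusion-related reactions that end dosing permanently) do not depend on an adjudication verdict. Only the joint entry does.

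**Step 2: route taken by a suspected, not yet adjudicated joint event.**

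| Event | Reporting route | Adjudication needed for prompt report? |
|---|---|---|
| Serious | 24 hours to the safety agent (11.2.6.1); a suspected serious drug reaction goes to the sponsor immediately (11.2.6.2) | No |
| Nonserious, any severity | eCRF, then to the sponsor under the Safety Management Plan (11.2.6.3) | Yes, under 11.3.1 as worded |

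The gap is confined to the second row.

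**Step 3: terms.**

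| Place | Joint terms |
|---|---|
| 11.3.1, AESI | RPOA (possible or probable), subchondral insufficiency fracture, primary osteonecrosis, pathological fracture |
| 9.3.1, stopping rule | destructive arthropathy |
| 5.3, composite joint endpoint from another programme | RPOA types 1 and 2, osteonecrosis, subchondral insufficiency fracture, pathological fracture |

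The AESI entities follow the composite in Section 5.3, apart from the restriction to primary osteonecrosis. The stopping term appears in neither of the other two lists and is not defined. Section 5.3 uses it once, beside RPOA and joined by 'or', which suggests a separate entity. The mismatch is therefore between Sections 9.3.1 and 11.3.1.

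**Step 4: neurogenic arthropathy.** It is named in exclusion criterion 10 and, taking neuropathic arthropathy to be the same condition, it is the reason for the mandatory radiographs. It does not appear among the AESIs.

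**Step 5: a contrast within the protocol.** For liver events, Appendix A works in the opposite order. Meeting the potential Hy's Law criteria triggers notification, and the causal assessment follows. If that assessment is unavoidably delayed beyond 3 weeks, the case is reported as a potential one. Suspicion is reported first and the verdict updates it.

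**The case against.** The strongest reply is that little can be missed. Serious suspected joint events, including important medical events under Section 11.1.4, are reported within 24 hours without adjudication. The stopping list is not exhaustive, so a drug-related serious or severe joint event falls under its parent criterion whether or not it has been adjudicated or called destructive arthropathy. Section 8.3 also lets the investigator withdraw a subject at any time. All of this stands, and it confines the reporting gap to nonserious events. It does not define the stopping term.

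A reader might infer that surveillance of joint events starts only after adjudication. The documents do not support that. Adverse events are collected at every visit, medical monitors review safety continuously, blinded aggregate data are reviewed about every 30 subjects and at least every 3 months (Section 9.3.1), and Section 13.1.6.1 tabulates all adverse events by preferred term. A neurogenic arthropathy would appear there even though it is not an AESI.

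A reader might also count exclusion criterion 10 as a third, conflicting definition. It is a medical-history criterion and need not match a list of on-study events.

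Two further points limit the finding. It is grammatically open whether the adjudication qualifier governs all four entities or RPOA alone; on the narrower reading the problem remains for RPOA, the event that Section 5.3 ranks first. The adjudication body, trigger and timing may also be set out in the Safety Management Plan or a charter that is not shown. Their absence here is no error, but such a document would not alter the AESI definition that this protocol gives investigators.

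**Conclusion.** The point holds in a limited form. Section 11.3.1 conflicts with itself for nonserious suspected joint events: immediate reporting is required whatever the seriousness, but the defining condition cannot be met at first awareness. Sections 9.3.1 and 11.3.1 use joint-event terms that do not map to each other, and the stopping term is undefined. The silence on neurogenic arthropathy is a gap against the protocol's own screening concern, which the sponsor should address explicitly; it is not a contradiction.

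The affected set is nonserious suspected joint events, from first awareness until positive adjudication. A reader might try to size it from the joint-event rates in Section 5.3. Those rates come from another drug and other populations, and they do not isolate nonserious events awaiting adjudication, so they do not measure this defect. No number can be given from the documents.

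The conclusion rests on a literal reading of the AESI entry and on the reporting routes as written in Section 11.2.6.

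**What to change.** Reword the joint entry in Section 11.3.1 so that any suspected event of the listed types is reportable at first awareness by the SAE procedure. Record the adjudicated outcome as a separate item and tabulate it separately from the suspected events.

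Reconcile the joint-event terms of Sections 9.3.1 and 11.3.1, and define destructive arthropathy if the term is kept. Which events stop treatment is a clinical decision for the sponsor, and no rule is proposed here. State explicitly whether neurogenic arthropathy is an AESI.

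The cost is amendment wording and a few additional expedited reports of events that adjudication later finds negative. Eligibility does not need to change.
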